During a telephone screening interview, potential participants will speak with a member of the research team to confirm study eligibility, to review details of the study protocol, and to enroll in the study if deemed suitable. During this discussion, potential participants will be given the opportunity to request an electronic copy of the informed consent form to review prior to meeting with the study team. Once enrolled, participants will attend an in-person testing session at one of the two trial locations. At this session, the research team will review: (1) the purpose of the study; (2) how the randomization process works; (3) a general overview of the testing conditions, and the self-report outcome measures. A thorough discussion of potential risks and benefits associated with participation in the study will then take place, as well as the assurance that participants may withdraw from the study or request a rest at any time during the study without consequence or without effect on the medical care that they receive. Each participant will be given a hard copy of

the informed consent form for signature and an extra copy to take home. Participants will be given as much time as required to re-read and complete the informed consent form, as well as the opportunity to ask for and receive clarification for questions as necessary.

Sample size

40 participants will be recruited for the present study. A power analysis based on COP excursion using a force plate with adults following a concussion has been calculated to determine the number of participants that need to be recruited for the present study. A change in COP excursion by more than 5cm will be considered to be significant, as this represents the minimal detectable change with a 90% confidence interval (Goble, Manyak, Abdenour, Rauh, & Bawega, 2016). A two-tailed analysis will be made with alpha level set at 0.05 and power set at 80%. Due to the nature of this crossover design, loss to follow-up is not expected, and therefore not accounted for in the sample size determination.

Randomization

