A force to the head or body that results in a concussion is of sufficient force to injure the soft tissue and joints of the cervical spine. Altered proprioception from injured cervical spine structures can contribute to symptoms of dizziness commonly associated with concussion. The NDI is the most commonly used self-report outcome measure for neck pain (MacDermid et al., 2009). The index is a simple and quickly administered 10-item questionnaire measured on a 6-point Likert scale from 0=no disability to 5 = full disability. Scores range from 0-50, with 50 representing the highest level of disability. Psychometric properties of scores demonstrate highly stable test-retest reliability (r=0.94-0.95) in patients with neck pain longer than 3 weeks (MacDermid et al., 2009). Clinically important difference have been reported with a 5-7 point change in score depending on whether the pain was of musculoskeletal or neural origin (MacDermid et al., 2009).

Saccadic eye function

Saccadic eye function will be assessed with two measures, a Tobii[™] Pro wearable eye tracker and the KDT. Tobii[™] Pro wearable eye tracker uses infrared videooculography to analyze patterns of eye movement in terms of fixations and saccades (www.tobiipro.com). Longer, more complicated visual tasks, such as rapid number naming, require longer processing times. The number of saccades completed during each balance condition will be recorded by the Tobii[™] Pro. The KDT is a vision-based test of rapid number naming speed that acts as a proxy measure for saccadic eye movement (Galetta, Liu, et al., 2015). The KDT consists of a demonstration card, plus a series of 3 increasingly more difficult test cards of variably spaced single digit numbers (Subotic et al., 2017). Following completion of the demonstration card, participants are asked to read each test card from left to right, top to bottom, as quickly as possible without errors. A summary score of the test is recorded as the total time to complete all 3 test cards, measured in seconds. Time to completion for the KDT will be recorded by the TobiiTM Pro. A meta-analysis demonstrated high test-retest reliability (ICC=0.92; CI_{95%}: 0.91, 0.94) in baseline trials (Galetta, Liu, et al., 2015).

Domain	Measure	Outcome of Interest		
		Baseline Disability	Primary	Secondary
Cervical spine	Neck Disability Index	Х		
Dizziness	Dizziness Handicap Inventory	Х		
Postural sway	M/L COP excursion		Х	
	A/P COP excursion		Х	
	95% ellipse COP		Х	

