For balance task B, participants will be asked to stand shoulder width apart on the BTS with their hands on their hips. Participants will be asked to complete a cognitive task while they maintain their balance. The visually based cognitive dual-task will involve the participants performing the King-Devick Test (KDT). Test cards will be fixed to a wall and positioned 12 inches from the participant's face at eye level. Participants will be asked to read the numbers out loud as quickly and as accurately as possible, from left to right, beginning at the top left corner of each test card. The total time to read all 3 test cards and the total number of errors committed will be recorded. If a participant makes an error, they will be asked to restart the test. The test usually takes less than two minutes to complete. Participants who complete the KDT in less than 2 minutes will be asked to restart the test from the beginning and continue reading for the remainder of the test period. Those individuals who require more than the allotted 2 minutes to complete the KDT will continue with the rapid number naming task until completion, and COP data will stop being collected at 2 min.

Throughout each trial, participants will be fitted with a pair of Tobii™ eye tracking glasses that will record their eye movements.

Control condition: normal vision

During the control arm of the trials, the eye tracking glasses will remain unobstructed and vision will not be occluded.

Experimental intervention: BNO

During the intervention arm of the trials, strips of occlusive material will be placed on the medial portion of each lens of the Tobii[™] eye tracking glasses to occlude central integrated vision.

Planned statistical analyses

Baseline characteristics for participants will be compared with descriptive statistics (mean, SD, n, %).

The primary objective, the effect of BNO on postural sway, will be addressed by using a dependent t-test to compare differences between treatment conditions for each COP variable. A similar analysis using a dependent t-test (group^xKDT_{time to} completion) will be performed to assess the secondary objective, the effect of BNO on reading. Additionally, a Wilcoxon Signed Rank test will be used to determine if there is a significant difference in the number of saccades completed on the KDT between

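### The two-period crossover is analysed with paired tests that ignore period; the tests are valid, but for King-Devick time a practice shift would cost precision that a period-adjusted analysis recovers cheaply

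*Protocol*

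**What the plan says.** The Design and Randomization sections describe a two-treatment, two-period crossover in which only the order of conditions is randomised. Forty participants are planned. The method of allocating sequences is not stated.

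Planned statistical analyses names the tests:

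- Centre of pressure (COP): "The primary objective, the effect of BNO on postural sway, will be addressed by using a dependent t-test", applied to each COP variable.
- KDT time: "A similar analysis using a dependent t-test". The bracketed group-by-KDT-time label beside it adds no period term, because the named test is still a paired one.
- Saccades on the KDT: "a Wilcoxon Signed Rank test will be used to determine if there is a significant difference in the number of saccades completed" between conditions.

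None of these uses sequence or period.

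On the task itself, Saccadic eye function describes one demonstration card and one series of three test cards, with no alternate set: "Following completion of the demonstration card, participants are asked to read each test card from left to right". Balance Testing Protocol adds two reasons for re-reading within a trial: "If a participant makes an error, they will be asked to restart the test", and early finishers must "restart the test from the beginning and continue reading for the remainder of the test period". The intervention arm repeats the same tasks as the control arm. Carryover is handled by a rest of at least one minute, or longer until symptoms settle.

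**The concern.** In a two-period crossover each participant's BNO-minus-control difference contains the treatment effect plus or minus any change from period 1 to period 2, with the sign set by the sequence. A paired test does not know the sequence, so a systematic change stays in the variance of the differences. The randomised sequence would allow it to be removed.

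Such a change is most plausible for KDT time. The same cards are used in both periods, and many participants will already have started them again before period 2. The demonstration card gives only some familiarisation, and rest does not undo practice.

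At stake are the width of the reported interval and the power for KDT time and, if the sequences turn out unequal, a displacement of the estimate.

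**Working it through.** **Inputs from the protocol.** N = 40, two-sided alpha 0.05 and 80% power (Sample size); test-retest ICC of KDT time 0.92, interval 0.91 to 0.94, from baseline trials (Saccadic eye function).

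**Inputs not in the protocol, therefore assumed.** The period shift (0, 0.25, 0.5 or 1 SDd), the true effect, and the sequence split.

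**The plan's own figure.** The sample size section says "A power analysis based on COP excursion using a force plate with adults following a concussion has been calculated", with a 5 cm change, but gives no SD, so 40 cannot be reproduced. Solving backwards, a paired t-test with N = 40 has 80% power for an effect of 0.454 SDd (5 cm with SDd of about 11.0 cm: 5/11.0 = 0.454). That effect size is the reference below. The 80% applies to COP excursion; no power is stated for KDT time or saccades.

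**Model.** For participant i, D = effect + s × shift + e, with SD(e) = SDd = 1 and s = +1 if BNO comes second, −1 if it comes first.

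**Step 1: interval width at 20/20.** The sample variance of D is on average 1 + shift² × 40/39, so the paired standard error is inflated by the square root of that:

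- 0.25: √(1 + 0.0641) = 1.03
- 0.5: √(1 + 0.2564) = 1.12
- 1: √(1 + 1.0256) = 1.42

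Simulation agrees. The mean 95% half-widths at shifts 0, 0.25, 0.5 and 1 are 0.318, 0.328, 0.356 and 0.453 SDd for the paired test, and 0.318 throughout for the adjusted analysis.

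**Step 2: power at 20/20.** The plus and minus shifts cancel in the mean, so its true standard error stays at 1/√40. Power is therefore about Φ(effect × √40 − 2.023 × inflation). For effect 0.454, effect × √40 = 2.871:

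- no shift: Φ(2.871 − 2.023) = 80%
- 0.25: Φ(2.871 − 2.087) = 78%
- 0.5: Φ(2.871 − 2.268) = 73%
- 1: Φ(2.871 − 2.879) = 50%

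Simulation (100,000 trials per scenario) gives:

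| Effect (SDd) | Paired t, shift 0 / 0.25 / 0.5 / 1 | Period-adjusted |
|---|---|---|
| 0.3 | 46 / 43 / 37 / 17% | 46% |
| 0.454 | 80 / 78 / 73 / 50% | 80% |
| 0.6 | 96 / 95 / 93 / 81% | 96% |
| 0.8 | 98% or more throughout | 99.9% |

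The paired type I error at 20/20 is 5.0 / 4.4 / 2.9 / 0.6%, so the test is conservative.

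**Step 3: unequal sequences.** The paired estimate moves by shift × (n1 − n2)/40, where n1 have BNO second and n2 have it first. With a 0.5 SDd shift, 22/18 gives 0.5 × 4/40 = 0.05 SDd (type I error 3.5%), and 25/15 gives 0.5 × 10/40 = 0.125 SDd (about 8%). Under simple randomisation a split of 25/15 or worse has probability 15%. Averaged over simple randomisation, the paired type I error is 4.9 to 5.0% at shifts from 0 to 1 SDd.

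**Step 4: scale.** The protocol cites "A meta-analysis demonstrated high test-retest reliability (ICC=0.92" with its interval. If that ICC carried over, SDd = √(2 × (1 − 0.92)) = 0.40 of the SD of KDT time (0.35 to 0.42 over the ICC interval). Shifts of 0.25, 0.5 and 1 SDd would then be 0.10, 0.20 and 0.40 SD of KDT time.

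**Step 5: saccades.** Treating the counts as normal with a constant shift, effect 0.454 SDd, signed rank power is 69 to 72% at shift 0.5 and 42 to 45% at shift 1 across separate simulations. The rank-sum test on period differences has 77 to 79%. This is indicative only.

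**The case against.** The strongest reply is that nothing here is an error: the design balances order, the paired tests are valid, and the harm depends on a shift the protocol never quantifies. Much of that stands. At 0.25 SDd the gain from adjusting is about 2 points at 20/20 and about 1 point averaged over simple randomisation; with no shift, adjusting costs about 1 point on that average. The ICC behind the scaling comes from baseline trials, its form is not stated, and restarts or person-to-person variation in response to BNO would enlarge SDd and make a given practice gain smaller in these units. The outcomes most exposed are secondary.

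Balance does not dispose of the point, however. It removes bias but leaves the shift in the paired standard error. The tests are also named in the protocol itself, so this is not a detail left to an analysis plan.

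Four stronger readings are tempting and not supported:

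- A reader might infer an inflated type I error from the 8% at 25/15. That figure is conditional on one uneven split; the average over simple randomisation is about 5%.
- A reader might infer that a 1 SDd shift is like losing half the sample. At 20/20 both analyses give the same estimate with the same true sampling error; only the reported interval is too wide.
- A reader might extend the interval argument to saccades. A signed rank test reports no interval by itself. Since early finishers read on to two minutes, even the direction of a practice effect on the count is unclear.
- A reader might extend it to COP, the primary outcome. A shift there is possible but not shown.

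**Conclusion.** The point holds as a low-cost improvement in efficiency, not as a correction of an invalid test. For KDT time the repeated cards make a practice shift plausible, and the planned paired t-test would turn it into a wider interval and lower power. The size rests on assumed shifts: 3% to 42% extra width, and power of 78% down to 50% instead of 80%, for shifts of 0.25 to 1 SDd at 20/20 with an effect of 0.454 SDd. The loss is trivial below 0.25 SDd and negligible for effects of 0.8 SDd. The adjustment also protects the estimate if the sequences are unequal. For saccades only power is in question; for COP the change is for consistency. Confidence is medium, because the protocol gives no information on the shift.

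**What to change.** In Planned statistical analyses, replace the paired tests as follows:

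- **KDT time and, for consistency, each COP variable:** compare the period-1-minus-period-2 differences between the two sequences with a two-sample t-test (effect = half the difference in means, 38 df). Alternatively, fit a mixed model with condition, period and sequence as fixed effects and participant as random.
- **Saccade counts:** compare the period differences between sequences with a rank-sum test.

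The cost is about two sentences of text and one degree of freedom (38 instead of 39), with no new data. If there is no shift, the power cost for an effect of 0.454 SDd is nil at 20/20, about 1 point averaged over simple randomisation (79.6% to 78.5%), and 2 to 3 points at 25/15 (80% to 77%), with rank-sum at about 74% against 78% for signed rank.
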